14.4.3. Trial Steering Committee (TSC)

The role of the TSC is to provide overall supervision of the trial. The TSC will review the recommendations of the Independent Data Monitoring Committee and, on consideration

of this information, recommend any appropriate amendments/actions for the trial as necessary. The TSC acts on behalf of the funder and the Sponsor.

14.4.4. Independent Data Monitoring Committee (IDMC)

The role of the IDMC is to provide independent advice on data and safety aspects of the trial. Meetings of the Committee will be held as required during the trial. This will include an assessment of safety once the maximum tolerated dose has been established, at which point toxicity data from the trial will be summarised in a report for the IDMC to review. The IDMC is advisory to the TSC and can recommend premature closure of the trial to the TSC.

Members of the IDMC will be required to sign an IDMC charter outlining their duties and responsibilities.

14.4.5. Safety Review Committee (SRC)

The Safety Review Committee will be comprised of the Chief Investigator, the clinical members of the TMG, 2 independent clinicians, the trial statistician and other relevant staff from UCL CTC. Their role is to perform DLT evaluation and review other relevant safety data to inform the decision of whether to escalate or de-escalate a cohort, continue recruitment in the current cohort or to suspend recruitment.

The SRC will meet in person and/or by teleconference as required to discuss safety data and to make decisions about dose escalation or de-escalation.

Members of the SRC will be required to sign a SRC charter outlining their duties and responsibilities.

14.4.6. Role of UCL CTC

UCL CTC will be responsible for the day to day coordination and management of the trial and will act as custodian of the data generated in the trial (on behalf of UCL). UCL CTC is responsible for all duties relating to safety reporting which are conducted in accordance with section 12 (Safety Reporting).

15. WITHDRAWAL OF PATIENTS

In consenting to the trial, patients are consenting to trial treatment, assessments, collection of biological samples, follow-up and data collection.

15.1. Withdrawal prior to Trial Treatment

If a patient will not have trial treatment, UCL CTC should be informed as soon as possible so that the cohort slot can be reallocated to another patient. The reason the patient was withdrawn must be recorded in the patient's notes and on the relevant Case Report Form(s). Reasons that a patient may not have trial treatment include:

- Issue with donor Tem apheresis or Tem product
- Patient does not have stem cell transplant
- Patient does not meet eligibility criteria for trial treatment (see section 6.2.3)
- Deterioration in health
- Patient or donor decision to withdraw consent

If a patient does not receive trial treatment, the Change of Status form should be completed and submitted to UCL CTC. The patient will be withdrawn from the trial and followed according to local practice. No further data will be collected.

15.2. Withdrawal of consent after Trial Treatment

If a patient withdraws consent for any aspect of study conduct after they have received treatment, the Change of Status form should be completed and submitted to UCL CTC.

15.2.1. Withdrawal of consent for follow up

If a patient withdraws consent for trial follow up, but is happy to continue with future data collection from hospital notes:

- They will remain on trial for follow up.
- The patient will no longer have trial-specific visits and assessments. Follow up forms should be completed based on the routine visit nearest the due date for the follow up form.
- The following CRFs must be submitted at time of withdrawal:
 - \circ Change of Status form
 - All CRFs up to and including the date of withdrawal of consent
- Thereafter, the site should report AEs/SAEs and DLTs as per sections 12.2 and 12.4 respectively, and all follow up forms, including notifications of relapse/progression and death.

15.2.2. Withdrawal of consent for data collection

If a patient explicitly states they do not wish to contribute further data to the trial their decision must be respected:

• The following CRFs must be submitted at the time of withdrawal:

- Change of Status Form
- o All CRFs up to and including the date of withdrawal of consent
- Thereafter no further data should be submitted, with the exception of SAE reports and DLT notifications as per section 12.2 and 12.4 (due to the requirements for oversight of safety)

15.2.3. Withdrawal of consent for use of samples

If a patient withdraws consent for the use of some or all of their samples in the trial or for future research, this should be reported on the Change of Status form. Unless the patient has also withdrawn consent for treatment/follow up, management and data collection should continue as per protocol.

15.3. Losses to Follow-Up

If a patient moves from the area, every effort should be made for the patient to be followed up at another participating trial site and for this new site to take over the responsibility for the patient, or for follow-up via GP. Details of participating trial sites can be obtained from the UCL CTC trial team, who must be informed of the transfer of care and follow up arrangements. If it is not possible to transfer to a participating site, the registering site remains responsible for submission of forms.

If a patient is lost to follow-up at a site every effort should be made to contact the patient's GP to obtain information on the patient's status.

16. TRIAL CLOSURE

16.1. End of Trial

For regulatory purposes the end of the trial will be when the final data item for the final patient is received by the UCL CTC (i.e. it is anticipated that this will be when the final patient completes their day 360 follow-up visit).. At this point the 'declaration of end of trial' form will be submitted to the Ethics Committee, as required.

Following this, UCL CTC will advise sites on the procedure for closing the trial at the site.

Once the end of trial has been declared, no more prospective patient data will be collected but sites must co-operate with any data queries regarding existing data to allow for analysis and publication of results.

16.2. Archiving of Trial Documentation

At the end of the trial, UCL CTC will archive securely all centrally held trial related documentation for a minimum of 25 years. Arrangements for confidential destruction will then be made. It is the responsibility of PIs to ensure data and all essential documents relating to the trial held at site are retained securely for a minimum of 25 years after the end of the trial, and in accordance with national legislation.

Essential documents are those which enable both the conduct of the trial and the quality of the data produced to be evaluated and show whether the site complied with the principles of GCP and all applicable regulatory requirements.

UCL CTC will notify sites when trial documentation held at sites may be archived. All archived documents must continue to be available for inspection by appropriate authorities upon request.

16.3. Early Discontinuation of Trial

The trial may be stopped before completion as an Urgent Safety Measure on the recommendation of the TSC or IDMC (see section 14.4.3 Trial Steering Committee (TSC) and 14.4.4 Independent Data Monitoring Committee (IDMC)). Sites will be informed in writing by UCL CTC of reasons for early closure and the actions to be taken with regards the treatment and follow up of patients.

16.4. Withdrawal from Trial Participation by a Site

Should a site choose to close to recruitment the PI must inform UCL CTC in writing. Follow up as per protocol must continue for any patients recruited into the trial at that site and other responsibilities continue as per the mNCA.

17. STATISTICS

17.1. Sample Size Calculation

The trial will be conducted as a dose-escalation study and use the Time-to-event Continual Reassessment Method (TITE-CRM; (17)) to guide dose-escalation decisions. The study aim is to identify the Maximum Tolerated Dose (MTD) and thus the Recommended Phase II Dose (RP2D) of Tem when given following allogenic stem cell transplantation. Four dose levels will be available for investigation $(1\times10^5/kg, 3\times10^5/kg, 1\times10^6/kg, 3\times10^6/kg)$. The MTD is defined as the largest dose of Tem that has an estimated risk of causing DLT (acute-pattern GvHD grade II-IV) equal or closest to 20% (the target toxicity level). We assume the relationship between DLT risk and Tem dose can be estimated using a two-parameter logistic model. Before the trial, we assume that the prior risk of DLT at the highest dose $(3\times10^6/kg)$ is 20%. We then use the prior calibration method of (18) to provide working prior beliefs for dose-toxicity risks at the other doses; this gives median DLT risks (and 90% credible intervals) shown in Table 1.

Dose	1x10⁵/kg	3x10⁵/kg	1x10 ⁶ /kg	3x10 ⁶ /kg
Prior median	8%	11%	15%	20%
90% Credible Interval	(0, 56)	(1, 63)	(1, 71)	(2, 78)

Table 1: Prior median probabilities of DLT risk per dose (90% credible interval). Model parameters (intercept and log-slope) from bivariate Normal distribution with means (-1.39, -1.17) and independent variances (2.60, 0.22) respectively.

A minimum of two patients will be treated at open dose cohorts. The first two patients will receive dose level 3 ($1x10^{6}$ /kg), and be followed for 72 days post infusion to monitor for GvHD onset. Data from patients 1 and 2 will be used to update the prior DLT risks, and a formal SRC meeting will be held to recommend the dose to be given to patients 3 and 4. After following up patients 3 and 4 for 72 days post infusion to monitor for GvHD onset, another formal SRC meeting will be held to recommend the dose to be given to patients 5 and 6. From then (after patient 5 and 6 begin treatment), partial follow-up data from the 72 day DLT window will be used to estimate DLT risks on an ongoing basis, so that new patients who are recruited before previous patients have completed follow-up may be entered onto the trial and receive Tem. Computations for updating the model will be performed in R Software(19).

The maximum sample size for this study is 18 patients. This was chosen based on projected recruitment timelines for eligible patients, and obtaining sensible operating characteristics from the design. The trial may be terminated early if either i) Tem dose is escalated to dose level 4 without any DLTs occurring and 6 patients are dosed at dose level 4 without experiencing DLT – dose level 4 will be declared as the MTD (total of 8 patients), or ii) the chance that the risk of DLT at the lowest dose being above the target toxicity level is at least 90% – the trial will be stopped for safety.

17.2. Statistical Analysis

17.2.1. Analysis of main endpoint

Occurrence of dose-limiting toxicity (DLT, defined as acute-pattern GvHD grade II-IV)

For DLT analysis, all patients deemed eligible for toxicity assessment will form the analysis population. Incidence of DLT per dose will be described in tables. GvHD data will be used to provide final estimates of DLT risks and their uncertainty using the dose-toxicity model. These estimates, along with SRC recommendations, will determine the MTD and thus RP2D of Tem.

17.2.2. Analysis of secondary endpoints and secondary analyses

Incidence and severity of acute GvHD (whether dose-limiting or not)

Incidence and severity of acute GvHD (dose-limiting or not), as defined by the Glucksberg Scale, will be reported per dose level in frequency tables.

Incidence and severity of chronic GvHD

Incidence and severity of chronic GvHD will be reported per dose level in frequency tables.

Non-relapse mortality at 1 year

Non-relapse mortality (NRM) is defined as the time from registration to time of death without relapse. NRM will be presented using a Kaplan-Meier (KM) plot (grouped across dose level and per dose level), and 1-year NRM rate will be estimated (with 95% confidence intervals).

Overall- and Event-free survival at 1 year

Overall survival (OS) is defined as the time from registration to time of death from any cause. Event-free Survival (EFS) is defined as time from registration to the occurrence of any of the following events: graft failure, disease relapse, disease progression, or time of death from any cause. OS and EFS will be presented using KM plots (grouped across dose level and per dose level), and 1-year OS and EFS rates will be estimated (with 95% confidence intervals).

Incidence/type of infection requiring inpatient admission at 1 year

Infections that require inpatient admissions from date of Tem Infusion until +360 days post-stem cell transplant will be documented, and the type of infection and duration of inpatient stays will be reported per dose level.

Total Number of inpatient days at 1 year

The median and range for the total number of days that patients spend in hospital as inpatients from the date of Tem Infusion up to 1 year post allo-SCT will be reported.

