The target population in this trial is patients undergoing an HLA-identical sibling haematopoietic stem transplant. The number of patients undergoing this procedure is 470/year in the UK, 5900/year in Europe and 2500/year in the US. The intended benefit of CD62L⁻ Tem transfer is to accelerate immune reconstitution in patients undergoing allo-SCT without incurring a greater risk of GvHD. Patients will therefore potentially benefit from improvements in clinical outcomes as a result of reduced non-relapse mortality secondary to infection. A reduction in hospital readmission and the need for additional treatments will help to improve the quality-of-life for patients. Reduced length-of-stay, re-admissions and drug costs could also reduce the financial burden to health care systems and increase value for money

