6.2.1. Patient Registration Inclusion criteria

- Severe aplastic anaemia or
- Primary immune deficiency or
- Haematological cancer which can be **ONE OF** the following (see Appendix 4 for complete response/remission (CR) and partial response/remission (PR) definitions):
 - $\circ~$ Non-Hodgkin's lymphoma (NHL) in CR or PR (and VGPR in applicable disease types)
 - Hodgkin's lymphoma (HL) in CR or PR
 - Chronic (Pro-)lymphocytic leukaemia (CLL or PLL) in CR, CRi or PR
 - Plasma cell myeloma (PCM) in CR, sCR, VGPR or PR
 - o Acute myeloid leukaemia (AML) in CR or CRi
 - Acute lymphoblastic leukaemia (ALL) in CR or CRi
 - Myelodysplastic syndrome (MDS) < 10 % blasts in bone marrow
 - Chronic myelomonocytic leukaemia (CMML) < 10% blasts in bone marrow
- Suitable for HLA-identical sibling transplant using a standard alemtuzumab-based conditioning regimen with calcineurin-inhibitor based immunoprophylaxis
- Aged \geq 16 years, <70 years
- Written informed consent

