6.2.3. Patient Trial Treatment Exclusion criteria

Following the stem cell transplant the following exclusion criteria must be checked within 2 days prior to the planned CD62L⁻ Tem infusion date. The patient's eligibility for trial treatment must be confirmed with UCL CTC prior to infusion taking place (see section 7.2) and continually assessed up to the point of Tem infusion.

- Prior or active acute pattern GvHD of any grade
- Relapse or progression
- Primary or secondary graft failure
- Has received other cellular therapies

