8.6. Follow Up after Graft Failure, Progression or Relapse

Patients with graft failure or that progress or relapse **during** the dose-limiting toxicity period will be followed up for the full 72 day DLT Follow Up Period (as per sections 8.4 and 9.4). Upon completing the DLT Follow Up Period these patients will no longer be required to attend days +100, +180, +270 and +360 post-stem cell transplant visits. The patient's status will continue to be collected on an annual basis from their stem cell transplant date.

Patients with graft failure or that progress or relapse **after** the dose-limiting toxicity period will no longer be required to attend the relevant remaining days +100, +180, +270 and +360 post-stem cell transplant visits. The patient's status will continue to be collected on an annual basis from their stem cell transplant date.

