Complete remission (CR)	The marrow is regenerating normal haematopoietic cells and contains <5% blast cells by morphology on the aspirate film. ANC ≥1.0 × 109/L; platelet count ≥100 × 109/L
CR with incomplete hematologic recovery (CR _i)	All CR criteria except for residual neutropenia (<1.0 × 109/L) or thrombocytopenia (<100 × 109/L)
Relapse	Not meeting criteria for CR or CRi

MDS and CMML

Note that response criteria are based upon eligibility of <10% blasts at study entry

Complete remission (CR)	The marrow is regenerating normal haematopoietic cells and contains <5% blast cells by morphology on the aspirate film. ANC ≥1.0 × 109/L; platelet count ≥100 × 109/L
CR with incomplete hematologic recovery (CR _i)	All CR criteria except for residual neutropenia (<1.0 × 109/L) or thrombocytopenia (<100 × 109/L)
Relapse	Not meeting criteria for CR or CRi

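### The NRM definition in section 17.2.2 leaves out progression, so read literally it counts deaths after disease progression as non-relapse mortality

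*Protocol*

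**What the plan says.** In section 17.2.2 of the protocol, "Non-relapse mortality (NRM) is defined as the time from registration to time of death without relapse". The 1-year rate is to be estimated with a 95% confidence interval, and Kaplan-Meier plots are to be shown for all dose levels together and for each one.

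The following paragraph of that section defines EFS by "graft failure, disease relapse, disease progression, or time of death from any cause", which keeps relapse and progression apart.

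Other sections also name both terms:
- Section 6.2.3, treatment exclusions: "Relapse or progression".
- Section 8.6, follow-up rules: "Patients with graft failure or that progress or relapse".
- Section 8.9 (therapy after disease failure) and section 12.2.2 (exemptions from SAE reports) each name both.
- Section 15.2.1, forms still due after withdrawal from visits: "including notifications of relapse/progression and death".

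On entry status, section 6.2.1 admits, for example, "Hodgkin's lymphoma (HL) in CR or PR". NHL, CLL/PLL and myeloma may likewise enter in partial response, and Appendix 4 allows Waldenström patients in VGPR or PR.

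**The concern.** NRM is meant to isolate deaths not due to the underlying disease. Section 2.1 says patients may benefit through "improvements in clinical outcomes as a result of reduced non-relapse mortality secondary to infection". If deaths that follow progression are counted as NRM, the endpoint mixes disease failure with the infectious and toxic deaths it is meant to show.

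The per-dose-level display makes this more awkward. Groups are very small and the eligible diseases differ in how failure is labelled. A dose level that happened to hold more lymphoid malignancies could show a higher NRM because of its disease mix and not because of the cell dose.

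The point concerns which deaths are events. It is separate from the choice of Kaplan-Meier and from the time origin, and a competing-risks estimator using the same definition would misclassify the same deaths.

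**Working it through.** The protocol gives no NRM rate, and no sample size or power based on NRM, so there is no stated figure to reproduce. The check is a comparison of texts, followed by arithmetic for scale.

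**Step 1: does relapse include progression?** In section 17.2.2 the NRM definition uses relapse alone, while EFS lists relapse and progression as two events. Sections 6.2.3, 8.6, 8.9, 12.2.2 and 15.2.1 also name both. The natural reading is that relapse on its own does not cover progression.

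**Step 2: which diseases does the omission touch?** Entry status comes from section 6.2.1 and Appendix 4, failure categories from Appendix 4.

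| Disease | Residual disease allowed at entry | Failure category in Appendix 4 | Affected |
|---|---|---|---|
| NHL, HL | Yes (PR) | Progressive disease only; regrowth of resolved lesions is placed there too | Yes |
| CLL/PLL | Yes (PR) | PD only | Yes |
| Waldenström / lymphoplasmacytic | Yes (VGPR, PR) | PD only | Yes |
| Myeloma | Yes (VGPR, PR) | PD, plus Relapsed/refractory (progression within 60 days of PR) and Relapsed (progression after a PR of more than 60 days, off therapy) | Narrowly: progression after 60 days while on therapy |
| AML, ALL | No (CR or CRi) | Relapse: "Not meeting criteria for CR or CRi" | No |
| MDS, CMML | Under 10% marrow blasts | Same relapse definition | No |

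**Step 3: would such deaths reach the data?** Yes. Section 8.6 keeps collecting patient status annually after progression, and section 15.2.1 shows that relapse, progression and death are all notified.

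**Step 4: scale.** As a crude proportion, one reclassified death shifts NRM by 1/n. The group sizes come from sections 8.3 and 17.1: at least 2 patients per open dose cohort, 6 at dose level 4 and 8 in total under the first early-stopping rule, and at most 18 overall.
- n = 18: 1/18 = 5.6 points
- n = 8: 1/8 = 12.5 points
- n = 6: 1/6 = 16.7 points
- n = 2: 1/2 = 50 points

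**Step 5: illustration.** Assume 18 patients, all followed to 1 year, with 2 deaths that had neither relapse nor progression before them. Let k be the number of deaths after progression that the literal wording adds. Crude NRM is (2 + k)/18, with Clopper-Pearson 95% intervals.

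| k | NRM | 95% CI |
|---|---|---|
| 0 | 2/18 = 11.1% | 1.4 to 34.7 |
| 1 | 3/18 = 16.7% | 3.6 to 41.4 |
| 2 | 4/18 = 22.2% | 6.4 to 47.6 |
| 3 | 5/18 = 27.8% | 9.7 to 53.5 |

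The counts are assumptions. The protocol gives neither the expected disease mix nor a rate of death after progression.

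**The case against.** The best defence is that relapse is shorthand here. Section 9.6 starts annual follow-up after progression alone, where section 8.6 gives the rule for graft failure, progression or relapse, so the protocol does sometimes let one word stand for more. An SAP may also spell out the event. This shows that the intention may be sound. It does not repair the text, because section 17.2.2 states the definition outright and contrasts the two terms in its next paragraph.

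A second objection succeeds in part. A reader might infer from Appendix 4 that a lymphoma or CLL patient can never relapse under this protocol. The documents do not support that. The appendix is invoked for status at entry (sections 6.2.1 and 9.1), and disease assessment during follow-up is by local policy (section 9.5). A site could record recurrence after a complete response as relapse. The problem is clearest for patients who enter in PR or VGPR and then progress.

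A reader might also take most myeloma progressions to be affected. They are not, since the two relapsed categories cover progression within 60 days and later progression off therapy.

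Finally, the intervals in the illustration overlap widely, and any single event moves a tiny group by 1/n. Both statements are true. They limit the consequence but do not justify the definition.

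**Conclusion.** The point holds as an error of definition with limited consequences. Followed literally, section 17.2.2 makes a death after progression an NRM event in lymphoma, CLL/PLL and Waldenström patients, and in the narrow myeloma group. Each such death adds 5.6 percentage points to crude NRM at 18 patients and 50 points in a dose level of two. These are crude proportions; the Kaplan-Meier shift would depend on timing and censoring. The conclusion rests on reading relapse as distinct from progression, as the EFS definition does.

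Two stronger readings are not supported. A reader might infer that dose decisions are at risk. They are not: under section 17.2.1 the MTD rests on the DLT estimates and the SRC's recommendations, and NRM carries no test or threshold. A reader might also infer that EFS needs the same repair, so that the two endpoints divide events cleanly. EFS already lists both events, and because it also counts graft failure, no clean division would follow.

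**What to change.** In section 17.2.2, define the NRM event as death from any cause without prior relapse or progression, so that a patient who relapses or progresses can no longer have an NRM event. Leave EFS as it is, and carry the same wording into any SAP.

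The cost is one amended sentence. Relapse, progression and death are already reported, so no new data, visits or forms are needed.

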1.3. Trial Schema

2. INTRODUCTION

2.1. Background

Following allogeneic stem cell transplantation (allo-SCT), a serious complication is graftversus-host disease (GvHD) which occurs as a result of immune injury to patient tissues mediated by donor T cells reacting to alloantigens (1, 2). It causes death in about 10% of patients and has a major negative impact upon quality-of-life in surviving patients (1, 2). Prevention of GvHD relies upon depletion of donor T cells or drugs that block T cell function. However, these strategies delay immune recovery, increase the risk of lifethreatening infection and lead to mortality in a further 10-15% of patients. A key challenge following allo-SCT is to accelerate immune reconstitution while at the same time avoiding GvHD. At UCL, we have run several trials to address this challenge involving the infusion of 1) positively selected, pathogen-specific T cells (e.g. CMV-IMPACT, NCT01077908) and 2) 'allo-depleted' T cells following in vitro removal cells activated upon exposure to recipient leukocytes (e.g. ICAT, NCT01827579). Routine use of these or other proposed strategies into normal clinical practice will not only depend upon their efficacy but also their complexity and cost; for this reason, there is an urgent need to test novel technologies that are both affordable and readily applicable.

Because alloreactivity is mainly derived from the naïve (or antigen inexperienced) T cell population (1, 2), one approach for separating GvHD-inducing T cells from pathogen-specific T cells is to select memory (or antigen experienced) T cells for adoptive transfer (3). Murine studies of allo-SCT have shown that memory T cells lacking surface expression of CD62L (CD62L⁻) are able to engraft following transplant and respond to pathogen challenge, but unlike the CD62L-expressing (CD62L⁺) T cells, do not induce GvHD (3). In addition to differences in T cell repertoire, memory T cells also possess repertoire-independent properties that limit their capacity to sustain effector cytokine synthesis and induce tissue injury (4). Human CD62L⁻ memory T cells also demonstrate reduced responses to allogeneic antigenic stimulation in vitro compared with CD62L⁺ T cells but maintain reactivity to viral antigens (5). These findings offer the opportunity of using memory T cells to enhance immune reconstitution following allo-SCT and provide broad immunity to multiple pathogens without the risk of GvHD.

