3.2. Trial Endpoints

Primary Endpoint

1. Occurrence of dose-limiting toxicity (DLT) (defined as acute-pattern GvHD grade II-IV)

Secondary Endpoints

- 1. Incidence and severity of acute GvHD (whether dose-limiting or not)
- 2. Incidence and severity of chronic GvHD
- 3. Non-relapse mortality at 1 year
- 4. Overall- and event-free survival at 1 year
- 5. Incidence/type of infection requiring inpatient admission at 1 year
- 6. Total number of inpatient days at 1 year

Biological Endpoints

- 1. TCR repertoire analysis by deep CDR3 sequencing
- 2. Chimerism and reconstitution of immune subsets
- 3. Reconstitution of virus- and bacterial-specific immunity
- 4. Relationship between donor demographics/immune profile with number of CD62L⁻ Tem selected.
- 5. Alemtuzumab levels on the day of CD62L⁻ Tem infusion

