8.9. Supportive Care

Prevention and management of infection

All patients should receive standard anti-microbial and anti-viral prophylaxis according to local policy to prevent infection by Pneumocystis carinii, encapsulated bacteria and herpes or varicella zoster re-activation. All at risk patients should undergo regular monitoring for CMV, EBV and adenoviral infection by peripheral blood PCR with preemptive therapy commenced according to local policy. All new respiratory infections should be screened by respiratory viral screening and where relevant sputum culture or bronchiolar lavage. Use of anti-fungals drugs as primary treatment or secondary prophylaxis will be according to local policy.

Relapse or progression

In the event of relapse or progression at any time point, patients will be eligible to receive additional therapy. Suitable therapies might include unmanipulated donor lymphocyte infusion (DLI), therapeutic antibody, small molecular inhibitors, epigenetic modifying agents, chemo- or radiotherapy or any combination thereof, according to local policy. Patients that progress or relapse post-Tem infusion will continue to be followed up as per sections 9.4 and 9.5.

Mixed chimerism

Determination of chimerism will be performed at Great Ormond Street Hospital NHS Trust to ensure uniformity throughout the trial and will be performed by PCR-STR. These assays will be performed according to standard operating procedures of the Central Laboratory and subject to internal quality control and quality assurance. The Central Laboratory participates in an external quality assurance scheme (UK NEQAS). Any patient who subsequently develops a significant fall in donor chimerism (defined as <50% donor chimerism) will be eligible to receive unmanipulated DLI or any alternative treatment as decided by the PI at each centre.

Unmanipulated DLI

In accordance with standard UK practice, all registered patients will be eligible to receive unmanipulated DLI from 6 months post-transplant if investigations confirm persistent disease or mixed chimerism. From 6 months post-transplantation, the risk of unmanipulated DLI causing GvHD is low if given according to an escalated dose regimen. An example of a conventional escalated dose regimen of unmanipulated DLI is 1×10^6 , 3×10^6 , 1×10^7 , 3×10^7 and 1×10^8 CD3 cells/kg at 10 week intervals provided patients have no evidence of active GvHD or prior acute GvHD grade II-IV.

Management of acute and chronic GvHD

See section 7

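### Non-relapse mortality is to be estimated by Kaplan-Meier although relapse is a competing event, so the 1-year rate can be overstated and is never understated

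*Protocol*

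**What the plan says.** Section 3.2 lists "Non-relapse mortality at 1 year" among six secondary endpoints. Section 17.2.2 defines it: "Non-relapse mortality (NRM) is defined as the time from registration to time of death without relapse". The same paragraph sets the method: "NRM will be presented using a Kaplan-Meier (KM) plot (grouped across dose level and per dose level), and 1-year NRM rate will be estimated". A 95% interval is planned for that rate. The paragraph does not say how a relapse enters the calculation, and it names neither competing risks nor cumulative incidence.

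The next paragraph of section 17.2.2 uses the same approach for the other two time-to-event endpoints: "OS and EFS will be presented using KM plots (grouped across dose level and per dose level". Relapse is one of the EFS events listed there, so its date is already needed.

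Section 17.1 caps the trial: "The maximum sample size for this study is 18 patients". Section 8.3 requires at least two patients in each open dose cohort.

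**The concern.** Kaplan-Meier suits OS and EFS because no other event prevents either from being observed. NRM differs, because relapse makes death without relapse impossible. Kaplan-Meier has no place for such an event except as censoring. Censoring assumes that a relapsed patient would have gone on to die without relapse at the same rate as those still at risk. One minus Kaplan-Meier then describes a hypothetical population in which nobody relapses, which is not the proportion of trial patients who die without relapse within a year.

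The protocol names the estimator itself, so a SAP that followed it would carry the problem forward. What is at stake is the accuracy of one reported safety outcome. The published 1-year NRM and its interval would refer to a different quantity from the one the endpoint names, would lean upwards, and would not be comparable with NRM reported elsewhere as a cumulative incidence.

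**Working it through.** **Inputs.** The protocol states no NRM rate, no relapse rate and no calculation based on NRM, so there is no figure of its own to reproduce. Section 2.1 says of GvHD "It causes death in about 10% of patients" and says that preventive strategies "lead to mortality in a further 10-15% of patients". These are general transplant figures and served only to choose an assumed range of true 1-year NRM, *n* = 10-25%. Relapse incidence, *r* = 0-40%, is purely an assumption. The maximum of 18 patients comes from section 17.1.

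**Formula (constant cause-specific hazards over one year).**
- Total hazard: H = -ln(1 - n - r)
- NRM hazard: h = H × n / (n + r)
- What Kaplan-Meier with relapse censored estimates: 1 - exp(-h)
- What Aalen-Johansen estimates: n

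Example with n = 0.15 and r = 0.30: H = -ln(0.55) = 0.598; h = 0.598 × 0.15/0.45 = 0.199; 1 - exp(-0.199) = 18.1%, against a true 15%.

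One minus Kaplan-Meier for each combination:

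| True NRM | relapse 0% | 10% | 20% | 30% | 40% |
|---|---|---|---|---|---|
| 10% | 10.0 | 10.6 | 11.2 | 12.0 | 12.9 |
| 15% | 15.0 | 15.9 | 16.9 | 18.1 | 19.6 |
| 20% | 20.0 | 21.2 | 22.5 | 24.2 | 26.3 |
| 25% | 25.0 | 26.5 | 28.3 | 30.4 | 33.2 |

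For true NRM of 10-20%, the excess is 0.6-1.2 points at 10% relapse and 2.9-6.3 points at 40% relapse.

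**Simulation, 18 patients, 20,000 replicates per scenario.**

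| True NRM / relapse | mean 1-KM | mean Aalen-Johansen | SD of Aalen-Johansen |
|---|---|---|---|
| 15% / 20% | 16.9% | 15.1% | 8.4 points |
| 15% / 30% | 18.1% | 15.0% | 8.4 points |
| 20% / 30% | 24.3% | 20.1% | 9.5 points |
| 25% / 40% | 33.3% | 25.0% | 10.2 points |

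One minus Kaplan-Meier was above the cumulative incidence in 84-98% of replicates and below it in none.

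**Worked examples (complete follow-up).**
- 18 patients, 5 relapses, 3 NRM deaths; cumulative incidence 3/18 = 16.7%. With all relapses first, 1-KM = 1 - (12/13)(11/12)(10/11) = 3/13 = 23.1%. With one interleaved order (NRM deaths at risk-set sizes 17, 14 and 11), 1-KM = 1 - (16/17)(13/14)(10/11) = 20.6%. With all relapses last, 1-KM = 16.7%, and the two agree.
- 6 patients at one dose level, 2 relapses then 1 NRM death: 1-KM = 1 - 3/4 = 25.0%, against 1/6 = 16.7%.
- 2 patients at one dose level, one relapse then one NRM death: 1-KM = 1 - 0/1 = 100%, against 1/2 = 50%.

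**The case against.** **The text does not say that relapse is censored.** It names Kaplan-Meier for the plot and then says that a rate will be estimated. If relapsed patients were kept in the risk set to the end of the year, with complete follow-up, one minus Kaplan-Meier would equal the cumulative incidence. This is true, but nothing in the protocol describes that handling. Reading the 1-year rate off a Kaplan-Meier curve with relapse censored is the natural interpretation, though it remains an inference.

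**The bias may be small.** Malignancies enter in response or with few blasts. Patients with aplastic anaemia or immune deficiency (section 6.2.1) have no malignancy to relapse. Relapse before infusion excludes a patient from treatment (section 6.2.3), and untreated patients contribute no further data (section 15.1). With 18 patients, one patient is 1/18 = 5.6 points, and the exact 95% interval for 3/18 runs from 3.6% to 41.4%. This stands and limits the severity. It does not make the estimator right: the interval is wide, but it surrounds the wrong quantity, and the error does not average out because it has one sign.

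**Stronger readings that a reader might infer.** One is that an inflated NRM would mislead the choice of phase II dose. Section 17.2.1 rules this out: the MTD, and with it the recommended phase II dose, comes from the dose-toxicity model and the Safety Review Committee. No NRM threshold, stopping rule or sample size exists. Another is that NRM and relapse would fail to add up to one minus EFS. That is not a valid test here, because EFS also counts graft failure and progression, so the sum need not match even with the correct estimator. Relapse incidence is also not a planned endpoint.

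**Conclusion.** The point holds as an error in the stated method, of minor to moderate severity. Section 17.2.2 assigns to NRM an estimator that cannot accommodate relapse. With relapse censored, the 1-year figure is at or above the cumulative incidence. The two are equal only when no relapse precedes an NRM death.

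The size depends on an assumed relapse rate, constant hazards and true NRM of 10-20%. On those terms the overstatement ranges from nothing without relapse to 6.3 points at 40% relapse, usually less than the sampling SD of about 8-10 points. The per-dose-level curves are the most exposed, since one early relapse in a handful of patients moves the figure considerably. The consequence is confined to the reporting of one descriptive secondary endpoint.

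**What to change.** In section 17.2.2, replace the Kaplan-Meier sentence for NRM with wording such as: *NRM will be presented as a cumulative incidence function (Aalen-Johansen), overall and per dose level, with relapse as the competing event, and the 1-year cumulative incidence will be estimated with a 95% CI.*

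State whether disease progression counts as relapse, and align the NRM definition with that choice. The current definition names only relapse, whereas EFS lists relapse and progression separately. Keep Kaplan-Meier for OS and EFS. Showing the cumulative incidence of relapse alongside is optional.

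The cost is a sentence or two of text and a routine analysis function. Only the time and type of each patient's first event are needed, and relapse dates are already required for EFS. No new data, visits or change in sample size follow.
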